1.0 Objectives

1.1 Describe the purpose, specific aims, or objectives of this research.

Response:

The purpose of this study is to compare the anxiety and pain levels of patients when using Buzzy with ice wings, Vapocoolant, and placebo during venipuncture procedure in pediatric patients.

1.2 State the hypotheses to be tested, if applicable.

NOTE: A hypothesis is a specific, testable prediction about what you expect to happen in your study that corresponds with your above listed objectives.

Response:

We hypothesize that the Buzzy will provide greater pain relief based on patient self-report and parent report of their child's pain as well as independent observation when compared to Vapocoolant or placebo.

2.0 Scientific Endpoints

2.1 Describe the scientific endpoint(s), the main result or occurrence under study.

*NOTE: Scientific endpoints are outcomes defined before the study begins to determine whether the objectives of the study have been met and to draw conclusions from the data. Include primary and secondary endpoints. Some example endpoints are: reduction of symptoms, improvement in quality of life, or survival. Your response should **not** be a date.*

Response:

Our primary outcome is that Buzzy will have a greater degree of reduction of anxiety and pain levels compared to vapocoolant or placebo.

3.0 Background

3.1 Provide the scientific or scholarly background, rationale, and significance of the research based on the existing literature and how it will contribute to existing knowledge. Describe any gaps in current knowledge. Include relevant preliminary findings or prior research by the investigator.

Response:

Among pediatric patients, phlebotomy and intravenous cannulation are two important sources of self-reported pain in the pediatric ED. Unmanaged needle stick pain has been associated with needle phobia, greater pain with future sticks; anxiety associated with other medical procedures, healthcare avoidance and increased adult pain sensitivity (Lunoe, 2014; Cohen 1997; Hamilton, 1995; Pate, 1996). Various methods have been proposed for management of acute pain associated with these medical procedures. Pharmacological methods include EMLA, lidocaine and ethyl chloride (vapocoolant). Behavioral methods such as information provision, distraction, sensory focusing, and cognitive behavioral therapy (CBT) have also been utilized (Blount, 2009). Optimization of pain control during phlebotomy and IV catheterization in the Pediatric ED is essential in an effort to avoid the aforementioned adverse effects of needle insertion. In the pediatric ED, quick acting methods are favored over those requiring time to act such as EMLA and CBT.

Vapocoolants, volatile refrigerated liquids such as ethyl chloride, are a frequent choice in many pediatric EDs, including our own, prior to phlebotomy or IV cannulation. Despite this, research has offered conflicting results as to their efficacy. Hogan and her colleagues conducted a systematic review of Vapocoolant in both children and adults and concluded that their "...results demonstrated that Vapocoolants are ineffective in children when compared to placebo or no treatment" (Hogan ,2014). Shah, Taddio & Rieder have hypothesized that the sensation of cold on their skin is perceived by children as painful (Shah, 2009).

Recently several labs have introduced hand held devices based on Melzack and Wall's Gait Control theory (Melzack 1965) which asserts that activation of non-nociceptive fibers can interfere with signals from pain fibers thereby inhibiting pain. This theory helps to explain why rubbing or massaging a painful area of skin can lessen the pain. One such device is the Buzzy.. The Buzzy is a vibrating palm-sized device with removable ice wings developed by MMJ Labs Atlanta, GA.

The Procedure Behavior Checklist (PBCL) is a well-established observational pain measure that has been validated for children 3-18 years old. It evaluates both the intensity and frequency of 10 defined behaviors that indicate distress. The PBCL was developed by Katz et al in 1980. On a scale of 1-5, it rates child's muscle tension, screaming, crying, restraint needed, verbalized pain, anxiety, etc. The scores are then added together to give a final score. The Faces Pain Scale – Revised (FPS- R; Hicks et al 1990) is a self-report measure used to assess the intensity of children's pain. It consists of 6 faces, with each one representing an increasing degree of pain moving from left to right in increments of two starting from zero (0, 2, 4, 6, ,8, 10).

Both of the PBCL and Faces pain scale –revised have been validated tool and used frequently in clinical practices and studies when evaluate patient's pain scale.

In this study, we will compare the effectiveness of pain release devices i.e. buzzy, with vapocoolants or placebo. We will use the validated PBCL and Faces pain scale-revised methods as the pain evaluation tools. To our knowledge, no study has been performed on comparison of the effectiveness of these commonly used pain release devices. We hope to contribute some useful information in this field through our research.

3.2 *Include complete citations or references.*

Response:

*Blount R. L., Zempsky W. T., Jaaniste T., Evans S., Cohen L. L., Devine K. A., Zeltzer L. K. Management of pain and distress due to medical procedures. In: Roberts M C, Steele R, editors. *Handbook of pediatric psychology*. 4th Ed. New York: Guilford Press; 2009. pp.171–188.*

Cohen Reis E. & Holubkov R. (1997). Vapocoolant spray is equally effective as EMLA cream in reducing immunization pain in school-aged children. Pediatrics, 100 (6).

Hamilton J.G. (1995). Needle phobia: A neglected diagnosis. Journal of Family Practice, 41 (2):169-175.

Hicks C.L., von Baeyer, C.L., Spafford P.A., van Korlaar I. & Goodenough B. The Faces Pain Scale - Revised: toward a common metric in pediatric pain measurement. Pain 93(2001) 173-183.

4.0 Study Design

4.1 Describe and explain the study design (e.g. case-control, cross-sectional, ethnographic, experimental, interventional, longitudinal, observational).

Response:

This is a single-center, randomized, open label, placebo controlled clinical trial.

5.0 Local Number of Subjects

5.1 Indicate the total number of subjects that will be enrolled or records that will be reviewed locally.

Response:

We will enroll 168 patients in the study with 56 in each arm.

5.2 If applicable, indicate how many subjects you expect to screen to reach your target sample (i.e. your screen failure rate).

Response:

We anticipate screening about 500 patients to reach our target sample.

5.3 Justify the feasibility of recruiting the proposed number of eligible subjects within the anticipated recruitment period. For example, how many potential subjects do you have access to? What percentage of those potential subjects do you need to recruit?

Response:

The Emergency Department at John R Oishei Children's Hospital has an annual volume of 45,000 to 50,000 patients, with at least 1/10 of them receiving venipunctures procedure including IV's line placement or phlebotomy procedure for various reasons. We anticipate that we can easily enroll 168 subjects within 24 months.

6.0 Inclusion and Exclusion Criteria

*6.1 Describe the criteria that define who will be **included** in your final study sample.*

NOTE: This may be done in bullet point fashion.

Response:

Inclusion criteria:

1. Male or female patients 6 to 18 years old

2. Need venipuncture procedure including IV's line placement and/or phlebotomy at the ED.

6.2 Describe the criteria that define who will be *excluded* from your final study sample.

NOTE: This may be done in bullet point fashion.

Response:

Exclusion criteria include:

1. Patients is sensitive to cold i.e. Raynaud's disease.
2. Sickle cell disease, diabetic
3. Critically ill patients
4. Mentally challenged patients
- 5.. GCS< 15
- 6.. Patient with altered sensation
- 7.. Patients needing more than one attempt for IV placement or phlebotomy

6.3 Indicate specifically whether you will include any of the following special populations in your study using the checkboxes below.

NOTE: Members of special populations may not be targeted for enrollment in your study unless you indicate this in your inclusion criteria.

Response:

- Adults unable to consent
- Individuals who are not yet adults (infants, children, teenagers)
- Pregnant women
- Prisoners

6.4 Indicate whether you will include non-English speaking individuals in your study. Provide justification if you will exclude non-English speaking individuals.

*In order to meet one of the primary ethical principles of equitable selection of subjects, non-English speaking individuals may **not** be routinely excluded from research as a matter of convenience.*

In cases where the research is of therapeutic intent or is designed to investigate areas that would necessarily require certain populations who may not speak English, the researcher is required to make efforts to recruit and include non-English speaking individuals. However, there are studies in which it would be reasonable to limit subjects to those who speak English. Some examples include pilot studies, small unfunded studies with validated instruments not available in other languages, studies with numerous questionnaires, and some non-therapeutic studies which offer no direct benefit.

Response:

This study will not include patients whose legal guardians do not speak English. Children with parents/legal guardians who cannot speak and read English will be encountered infrequently. They represent diverse language groups and translating consent documents as well as translating pain scale surveys into many languages would be impractical for this unfunded study. Meanwhile, it is impractical for us to have two people who speak the same non-English language during the recruitment phase with one being the person who obtains the consent and one being the witness per our IRB request at any given time.

By not including non-English speaking subjects in this study, we are not withholding any benefit from these patients. Meanwhile, we do not anticipate that we add any burden to the patients who are enrolled in the study.

The main purpose of this study is to compare the effectiveness of pain relief using different methods, the Buzzy, vapocoolant and placebo. Patient enrolled in the study will randomly assigned into one of the three different study groups, Buzzy Bee with ice wings, vapocoolant or placebo. For eligible patients that are not enrolled in the study, they may also receive buzzy, or vapocoolant intervention, depending on the bedside nurse's discretion, as these methods have been frequently used by our ED nurses to help patients for pain relief. So regardless weather a patient is enrolled in the study or not, he/she may receive the similar pain relief method for IV line placement or phlebotomy procedure.

Thus, we will exclude subjects whose legal guardians do not speak English from the study due to the above mentioned reasons. We believe that we will not withhold any benefit from non-participants, nor add any burden to the participants by not enrolling non-English speaking patients in the study.

7.0 Vulnerable Populations

If the research involves special populations that are considered vulnerable, describe the safeguards included to protect their rights and welfare.

NOTE: You should refer to the appropriate checklists, referenced below, to ensure you have provided adequate detail regarding safeguards and protections. You do not, however, need to provide these checklists to the IRB.

7.1 *For research that involves **pregnant women**, safeguards include:*

NOTE CHECKLIST: Pregnant Women (HRP-412)

Response:

N/A: This research does not involve pregnant women.

7.2 *For research that involves **neonates of uncertain viability or non-viable neonates**, safeguards include:*

NOTE CHECKLISTS: Non-Viable Neonates (HRP-413), or Neonates of Uncertain Viability (HRP-414)

Response:

N/A: This research does not involve non-viable neonates or neonates of uncertain viability.

7.3 For research that involves **prisoners**, safeguards include:

NOTE CHECKLIST: *Prisoners (HRP-415)*

Response:

N/A: This research does not involve prisoners.

7.4 For research that involves **persons who have not attained the legal age for consent to treatments or procedures involved in the research (“children”)**, safeguards include:

NOTE CHECKLIST: *Children (HRP-416)*

Response:

We will obtain consent from legal guardian for subject who is younger than 18 years of age.

N/A: This research does not involve persons who have not attained the legal age for consent to treatments or procedures (“children”).

7.5 For research that involves **cognitively impaired adults**, safeguards include:

NOTE CHECKLIST: *Cognitively Impaired Adults (HRP-417)*

Response:

N/A: This research does not involve cognitively impaired adults.

7.6 Consider if other specifically targeted populations such as students, employees of a specific firm, or educationally or economically disadvantaged persons are vulnerable. Provide information regarding their safeguards and protections, including safeguards to eliminate coercion or undue influence.

Response:

No other specifically targeted populations will be enrolled in this project.

8.0 Eligibility Screening

8.1 Describe **screening procedures** for determining subjects’ eligibility. Screening refers to determining if prospective participants meet inclusion and exclusion criteria.

 *Include all relevant screening documents with your submission (e.g. screening protocol, script, questionnaire).*

Response:

We will use a screening sheet to help our physician identify patient’s eligibility. The screening sheet is the first page of the data collection form.

N/A: There is no screening as part of this protocol.

9.0 Recruitment Methods

N/A: This is a records review only, and subjects will not be recruited.

NOTE: If you select this option, please make sure that all records review procedures and inclusion/exclusion screening are adequately described in other sections.

9.1 Describe when, where, and how potential subjects will be recruited.

NOTE: Recruitment refers to how you are identifying potential participants and introducing them to the study. Include specific methods you will use (e.g. searching charts for specific ICD code numbers, Research Participant Groups, posted advertisements, etc.).

Response:

Our study team will screen potential eligible patient by monitoring the patients' Tracking Shell (OCH All Beds Only view) in the password protected Power chart system at the ED of John R. Oishei Children's Hospital. Patient needs blood work or IV fluid /medication treatment will be screened for eligibility.

9.2 Describe how you will protect the privacy interests of prospective subjects during the recruitment process.

NOTE: Privacy refers to an individual's right to control access to him or herself.

Response:

Our research team will approach the patient and the legal guardian in a patient's private room at the ED. The consent process will be done when no other staff is in the room.

9.3 Identify any materials that will be used to recruit subjects.

NOTE: Examples include scripts for telephone calls, in person announcements / presentations, email invitations.

 For advertisements, include the final copy of printed advertisements with your submission. When advertisements are taped for broadcast, attach the final audio/video tape. NOTE: You may submit the wording of the advertisement prior to taping to ensure there will be no IRB-required revisions, provided the IRB also reviews and approves the final version.

Response:

No materials will be used for recruitment for this study.

10.0 Procedures Involved

10.1 Provide a description of all research procedures or activities being performed and when they are performed once a subject is screened and determined to be eligible. Provide as much detail as possible.

NOTE: This should serve as a blueprint for your study and include enough detail so that another investigator could pick up your protocol and replicate the research. For studies that have multiple or complex visits or procedures, consider the addition of a schedule of events table in in your response.

Response:

Randomization of subject into one of the three study arms

There will be three arms of this study with each arm testing a different pain reducer: Buzzy Bee, Vapocoolant, and placebo. We will use a sham device e.g. a band around the arm for placebo control.

After obtaining informed consent, the patients will be randomized into one of the three groups following a randomization table created by a statistician. Whichever intervention is randomly selected will be performed on patient prior to the needle stick.

These methods have been used in the ED as part of routine procedures to help patient for pain relief from a needle stick, the RNs are familiar with these methods. However, for the purpose of this study, the training videos will be uploaded in the Kaleidoscope Talent management for RNs to review the procedure and help them to refresh their memories.

Videotaping of subject

Using a camera, an ED research assistant will videotape subject's whole body including the facial expression while phlebotomy and IV catheter placement is performed for scoring of the PBCL. We will tape the entire venipuncture procedure starting from sterilization and ending at the time when the venipuncture is completed. If the first venipuncture procedure attempt is failed, we will not tape the second attempt. This subject will be withdrawn from the study.

Obtaining pain scores from subject and legal guardian using the Faces Pain Scale-Revised instrument

Before and after the venipuncture procedure, we will ask the legal guardian and subject to complete a Faces pain scale revised form. Since the revised form is validated to use for both adult and children, the same document will be used for the legal guardian and children for this study. This document is attached with this submission.

Reviewing of the videotape

Two physicians will review the video tape independently, and give a score using the PBCL tool. These two physicians are blinded to the study aims. They will be trained on how to use the PBCL by the PI.

In the event when there is a discrepancy of the PBCL score between the two reviewers, the mean of the two scores will be used as the final score.

10.2 Describe what data will be collected.

NOTE: For studies with multiple data collection points or long-term follow up, consider the addition of a schedule or table in your response.

Response:

We will collect demographic data, reason for venipuncture, PBCL score, facial pain score etc.

10.3 List any instruments or measurement tools used to collect data (e.g. questionnaire, interview guide, validated instrument, data collection form).

Include copies of these documents with your submission.

Response:

The following documents will be used for data collection:

1. Data collection form

2. Procedure behavior check list (PBCL)
3. The Faces Pain scale-revised document.

These documents will be submitted with this IRB application.

10.4 Describe any source records that will be used to collect data about subjects (e.g. school records, electronic medical records).

Response:

Kaleida health Electronic power chart records will be used for data collection.

*10.5 Indicate whether or not **individual** subject results, such as results of investigational diagnostic tests, genetic tests, or incidental findings will be shared with subjects or others (e.g., the subject's primary care physician) and if so, describe how these will be shared.*

Response:

No individual subject results will be shared with the subject or others.

*10.6 Indicate whether or not **study** results will be shared with subjects or others, and if so, describe how these will be shared.*

Response:

Study results will not be shared with subjects or others. The final results of this study may be presented at a conference or published in a peer reviewed journal; however, only group data will be publicized in these circumstances, no individual identifiable information will be released.

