17.0 Data Management and Analysis

17.1 *Describe the data analysis plan, including any statistical procedures. This section applies to both quantitative and qualitative analysis.*

Response:

All data analyses will be performed with SAS (version 9.2; SAS Institute, Inc., Cary, NC) and R (version 3.0.3) software. Chi-square and Fisher's exact test will be used to compare adverse events (e.g., systemic reaction, anaphylaxis, SOB, dyspnea, excess bleeding or hematoma formation), venipuncture and catheterization first attempt success, and number of patients with no to mild pain during needle insertion.

The Kruskal-Wallis test will be used to compare each of the two observers' assigned scores on the PBCL across three time periods: pre, procedure and post-procedure. Pre-procedure is defined as the time period prior to needle insertion including the placement of Vapocoolant, pain control or sham device up to needle insertion. The procedure period is defined as needle insertion through withdrawal. Post-procedure is defined as the 2 minute time period after needle withdrawal. Only patient and observer pain scores will be used for first-time needle insertion. If first attempt is failed, subject will be withdrawn from the study. Comparisons of pain scores of the five intervention groups to placebo (sham device) will be analyzed via ANOVA.

17.2 If applicable, provide a power analysis.

NOTE: This may not apply to certain types of studies, including chart/records reviews, survey studies, or observational studies. This question is asked to elicit whether the investigator has an adequate sample size to achieve the study objectives and justify a conclusion.

Response:

For chi-square analysis, based on a medium effect size of 0.3, alpha of 0.05, degree of freedom of 8, and 80% power it is estimated we will need a total of 168 subjects (56 per group). (*QFAB Bioinformatics*. 2015)

17.3 Describe any procedures that will be used for quality control of collected data.

Response:

Our RA will double check the data form to assure accuracy and completeness of data collection, if there is any missed data point, the RA will fill in the missing information immediately.

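### The binary outcomes are tested without adjusting for IV placement versus phlebotomy; a procedure-stratified test would be a cheap, modest gain (minor)

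*Combined protocol and SAP*

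**What the plan says.** Section 6.1 takes children aged 6 to 18 who "Need venipuncture procedure including IV's line placement and/or phlebotomy at the ED". The two procedures may overlap, and no expected split is given.

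Section 10.1 says that "the patients will be randomized into one of the three groups following a randomization table created by a statistician". It names no strata, block sizes or method of concealment, and it does not say that the table is unstratified. Section 5.1 plans 1:1:1 allocation: "We will enroll 168 patients in the study with 56 in each arm".

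Section 17.1, repeated in the unnumbered analysis text at the end of the document, says: "Chi-square and Fisher's exact test will be used to compare adverse events". The same test family covers "venipuncture and catheterization first attempt success, and number of patients with no to mild pain during needle insertion". No adjustment for procedure is named for any outcome. PBCL scores go to Kruskal-Wallis and pain scores to ANOVA.

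Section 17.2 sizes the trial for a chi-square analysis, "based on a medium effect size of 0.3, alpha of 0.05, degree of freedom of 8, and 80% power".

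**The concern.** Cannulation and phlebotomy may differ in needle pain and in first-attempt success. The planned procedure should usually be known before allocation: section 9.1 screens for children who need blood work or IV treatment, and section 10.2 already collects the reason for the venipuncture. The plan acknowledges both procedures but never says how they enter the arm comparison.

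A plain chi-square leaves between-procedure variation in the noise. If procedure predicts the outcome, a test that compares arms within procedure is more powerful with the same patients. It also gives a pre-planned answer if the arms happen to differ in procedure mix. An adjustment chosen after such a difference has been seen carries less weight.

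**Working it through.** **1. The plan's own figure.** For a chi-square test, N = λ/w², where λ is the noncentrality that gives the stated power. With df 8, alpha 0.05 and 80% power (section 17.2), λ = 15.02, so N = 15.02/0.09 = 166.9. Three equal arms make this 168, with power 80.3%. The figure reproduces. A comparison of three arms on a yes/no outcome has df (3 − 1)(2 − 1) = 2, however. At w = 0.3 that needs N = 107.05, or 108, and 168 gives 94.6% power before withdrawals.

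**2. Chance imbalance in procedure mix.** If a share p of children need an IV, the SD of the difference in IV share between two arms of 56 is √(2p(1 − p)/56). This is 9.4 points at p = 0.5 and 8.7 points at p = 0.3. Among three arms, the largest gap exceeds 15 points in about 24% of trials at p = 0.5 and 18% at p = 0.3 or 0.7. The values of p are assumptions.

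**3. Does imbalance invalidate the test?** With three arms, simple randomization and procedure odds ratios from 1 to 5, the plain chi-square has a simulated type I error of about 0.048 to 0.054. In the two-arm contrast of step 5 it is about 0.046 to 0.048. The test is valid on average. Among the roughly 11% of two-arm contrasts where IV share differs by more than 15 points, the false-positive rate is higher: 6.1%, 7.8% and 13.7% at procedure odds ratios of 2.3, 3.4 and 9.

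**4. Power, three arms of 56** (simulation, 40,000 trials per scenario). Assumptions: IV share 30% or 50%; no-to-mild pain 30% or 50% in two arms; the third arm better by an amount that gives the plain chi-square about 76 to 80% power. The gain from a stratified table plus Cochran-Mantel-Haenszel (CMH), over simple randomization plus chi-square, is:

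| Odds ratio, procedure on outcome | Gain (points) |
|---|---|
| 1 | about 0 |
| 2 | about 0.5 to 1 |
| 3 | about 1 to 2 |
| 5 | about 4 to 6 |

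**5. Which change produces the gain?** For one 56-versus-56 contrast, assume half the children need an IV and a within-procedure log odds ratio of 1.1 between arms (200,000 draws). The procedure odds ratio follows from the assumed rates of no-to-mild pain; for example, (0.65/0.35)/(0.35/0.65) = 3.4.

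| IV / phlebotomy rate | Odds ratio | Simple table, chi-square | Simple table, CMH | Stratified table, CMH |
|---|---|---|---|---|
| 45% / 65% | 2.3 | 74.5% | 75.0% | 75.6% |
| 35% / 65% | 3.4 | 72.1% | 75.6% | 76.3% |
| 25% / 75% | 9 | 57.5% | 69.0% | 69.1% |

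Changing only the test gains 0.5, 3.5 and 11.5 points. Stratifying the table as well adds 0.6, 0.7 and 0.1. The three-arm runs agree: at an odds ratio of 5, with IV share and base rate of 30% and 50% in one order or the other, power is 0.794 with chi-square, 0.847 with CMH alone and 0.848 with both.

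**6. Stratifying without adjusting.** If the table is stratified but the plain chi-square is kept, type I error in the step 5 scenarios falls to about 4.1%, 3.7% and 2.2%. In the three-arm runs it is 3.1 to 3.4% at an odds ratio of 5. The test becomes conservative and power barely moves.

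**The case against.** The defence of the plan is strong on several counts.

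- **Chance imbalance is not bias.** Ordinary sampling variation in procedure mix is already covered by the test's error rate (step 3). This stands. The higher error in visibly unbalanced trials is a reason to plan an adjustment, not evidence of an invalid test.
- **Nothing shows that procedure matters.** The documents give no IV share, no rates by procedure and no evidence of an effect. This stands. The 11.5-point gain needs an odds ratio of 9, which is extreme.
- **The reach is narrow.** The primary outcome in section 2.1 is anxiety and pain levels, scored mainly by PBCL and the Faces scale and analysed by other methods. First-attempt success has a separate problem: sections 20.1 and 20.2 withdraw failures and collect no data from them, which stratification does not cure. Adverse events may be too sparse to stratify. That leaves chiefly no-to-mild pain.
- **There is no shortfall on the plan's own terms.** With df 2 and w = 0.3, 168 patients give 94.6% power.
- **The plan may already separate the procedures.** The wording on first-attempt success could mean results by procedure. That is possible, but it says nothing about the pain outcome.

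What remains is efficiency: a better test is available at almost no cost.

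**Conclusion.** The point holds as a minor refinement of the analysis. The unadjusted comparison is valid but gives up power if procedure type predicts no-to-mild pain. In the three-arm setting the gain from adjusting is about 0 to 2 points up to an odds ratio of 3 and about 4 to 6 points at 5, and it is larger only at extreme values. The two-arm contrast gives a total of 4.2 points at 3.4, so the size also depends on which comparison is made. Every power figure rests on assumed rates and on full arms of 56.

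A reader might infer more: that the table is known to be unstratified, that this biases the binary comparisons, or that it leaves them underpowered. The documents do not support any of these. Section 10.1 is silent on strata, and silence does not establish that there are none. Type I error is held under simple randomization. The stated sample size does not depend on stratification. Whatever power is lost is lost in the analysis, and a stratified table alone would not recover it.

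**What to change.** **Main change.** Record the planned procedure (IV placement, with or without a blood draw, versus phlebotomy only) before allocation. In section 17.1, and in the repeated text at the end of the document, pre-specify a CMH test or logistic regression stratified by procedure for no-to-mild pain. Keep Fisher's exact test for sparse adverse events.

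**Optional.** In section 10.1, have the statistician stratify the table by planned procedure. Use randomly varying block sizes large enough to limit predictability in this open-label, single-center trial, and conceal the next assignment from the research assistants who enrol. This adds under 1 point of power and serves mainly to avoid visible imbalance. If it is done, the analysis must include the strata (step 6).

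**Cost.** One sentence in 17.1 and one extra item recorded before allocation; no more patients. If procedure turns out not to matter, CMH on an unstratified table loses about 0.4 to 0.7 points in the three-arm runs. The optional step means two allocation sequences and some added risk that assignments can be guessed.
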